7.7 Pregnancy

If the study subject is the father, then two forms should be completed, one for the father and the other for the mother and neonate. To ensure subject safety each pregnancy must also be reported to Merck within 15 days of learning of its occurrence.

Pregnancies and lactations that occur in a study subject or in a study subject's partner from the time of treatment allocation through 120 days following cessation of study treatment, or 30 days following cessation of treatment if the subject initiates new anticancer therapy, whichever is earlier, must be reported by the investigator to the Central Office within 24 hours of learning of the event. Central Office will report pregnancy to Merck Global Safety. (Attn: Worldwide Product Safety; [contact]) within 2 working days. All reported pregnancies must be followed up to determine outcome, including

spontaneous or voluntary termination, details of birth, and the presence or absence of any birth defects, congenital abnormalities or maternal and newborn complications.

7.8 Investigator Notifications

The Sponsor-Investigator will receive Investigator Notifications (INs) issued by Merck for suspect, unexpected SAEs which have occurred in Merck-sponsored studies with the study drug. The Sponsor-Investigator is responsible for forwarding these INs to all sub-investigators participating in the study, as well as to the Research Ethics Boards, according to local practice.

7.9 Data Safety and Monitoring Board

A Data Safety and Monitoring Board, an independent group of experts, will be reviewing the data from this research throughout the study to see if there are unexpected or more serious side effects than described in the consent. For this study, the Drug Development Program DSMB will be fulfilling this role.

8. PHARMACEUTICAL INFORMATION

A list of the adverse events and potential risks associated with the investigational agents administered in this study can be found in Section 7.1.

8.1 Investigational Agent - Pembrolizumab

Pembrolizumab will be provided by Merck as a liquid solution (100 mg/4mL vial) in Type I glass vials intended for single use only. The drug product is stored under refrigerated conditions (2 to 8°C).

The liquid drug product can be further diluted with normal saline or 5% dextrose in the concentration range of 1 to 10 mg/mL in intravenous (IV) containers made of polyvinyl chloride (PVC) or non-PVC material. Diluted pembrolizumab solutions may be stored at room temperature for a cumulative time of up to 4 hours. In addition, IV bags can be stored at 2 to 8°C for up to a cumulative time of 20 hours. Refer to pharmacy manual for more information.

Pembrolizumab Manufacturing

Merck manufactures Pembrolizumab for clinical use.

Pembrolizumab Packaging and Labeling

Clinical supplies of pembrolizumab will be affixed with a clinical label in accordance with regulatory requirements.

Pembrolizumab Handling and Storage

Investigational agent will be stored under secure (with limited access), and temperature-controlled conditions specified on the label for the duration of the study. Receipt and dispensing of trial medication

must be recorded by an authorized person at the trial site.

Pembrolizumab Ordering and Shipping

Pembrolizumab will be supplied by Merck to the study site. The Principal Investigator, or authorized study personnel, upon receipt of the study medication supplies, will conduct an inventory and acknowledge receipt to Merck, or designee.

Study medication should only be dispensed once a subject has (1) signed an informed consent form (ICF), (2) met all eligibility criteria for entry into the study, (3) completed all screening and continuing eligibility requirements, and (4) been assigned a subject identification number.

Agent Accountability

The Investigator is responsible for study medication accountability, reconciliation, and record maintenance. In accordance with all applicable regulatory requirements, the Investigator or designated study personnel must maintain study medication accountability records throughout the study.

The accountability records maintained during the study will be used to support subject dosing data. Site personnel are responsible for reconciling and resolving discrepancies in study medication accountability.

Missing study medication must be recorded along with an explanation of the discrepancy. At the conclusion of the study, all unused study medication and all medication containers will be destroyed locally as per UHN destruction policy.

Agent Inventory Records

The investigator, or a responsible party designated by the investigator, must maintain a careful record of the inventory and disposition of all agents received using their site-specific Drug Accountability Record Form (DARF).

9. BIOMARKER, CORRELATIVE, AND SPECIAL STUDIES

Biomarker analyses in this study will be exploratory.

9.1 Tumor Biopsies

A pre-treatment biopsy will be performed in all patients enrolled. The biopsy should be performed at any time during the screening period before cycle 1, day 1 once informed consent has been signed. The biopsy will be conducted according to institutional guidelines using standard surgical techniques. 4 cores will be obtained.

Tumor material will be prioritized as follows:

1. Whole exome sequencing
2. Whole transcriptome sequencing
3. PD-L1 expression and TIL analysis
4. Methylation profiling

*In the event that a patient has not had a biopsy to determine clinical diagnosis prior to study entry the first core must be prioritized for this. This will require a review by a pathologist of collected samples.

An optional post treatment biopsy will take place between weeks 3-6 and tissue will be banked.

9.1.1 MOLECULAR ANALYSES AND DATA EVALUATION

9.1.1.1 WES of Tumor DNA

WES of tumor DNA and germline DNA will be performed in OICR with already established protocol using next generation DNA sequencing. Data generated will be analyzed using established bioinformatics pipelines to study somatic mutations and derive potential mutational signatures. These results should be available within 8 weeks of baseline fresh tumor biopsy.

Germline mutations detected in study subjects will be reported to the co-investigator (treating physician) to facilitate clinical confirmation of mutation(s). Participants with pathogenic germ line mutations identified through the study and who have consented to be informed of genetic information will be approached by the study genetic counselor (Canadian and American board certified). The research results disclosure session will consist of genetic counseling about the research finding and need for confirmation testing. The session will also summarize gene specific risks and inheritance pattern. The study genetic counselor will offer confirmation testing of the research finding through a clinically accredited laboratory. When clinical confirmation results are available, these will be disclosed to the participant and their treating physician by the genetic counselor. Clinical results disclosure session will summarize gene specific cancer risks, inheritance, surveillance for early detection and/or surgical interventions for prevention, and procedures for testing family members.

9.1.1.2 RNAseq of Tumor

Whole transcriptome sequencing of tumor RNA will be performed using next generation sequencing in OICR with established protocols (see Lab Manual). RNAseq data will be used to perform exploratory analysis. Planned analyses include evaluation of differences in gene expression levels between responders and non-responders to study treatment. Further exploratory analyses will include interrogation of inflammatory signatures. In patients consenting for a second optional biopsy, immune signatures will be compared pre and post treatment.

9.1.2 PD-L1 and Immunoscore

Tumor samples from this study will be analyzed for percentage PD-L1 expression. PD-L1 protein level, as assessed by IHC in tumor sections, has been shown to correlate with response to pembrolizumab in subjects with NSCLC, and a PD-L1 IHC diagnostic is marketed for use with pembrolizumab in NSCLC. Preliminary data indicates that this association may also be true in additional cancer types (i.e., triple-negative breast cancer, head and neck, and gastric). The burden of tumor-infiltrating lymphocytes (TILs) may also predict response to ICIs and provide an ‘immunoscore’ which can prognosticate in HCC; densities of CD8, CD3, CD45R0 and PD-1 will also be assessed.^{65,66} This will be performed by QualTek Molecular Laboratories, Pennsylvania.

9.1.3 Methylation Profiling

DNA extracted from tumor biopsies will be delivered to the [name] laboratory at the Princess Margaret Cancer Centre for DNA methylation mapping. Tumor methylation profiling will be correlated with that seen in cfDNA. (Section 9.2.1)

9.1.4 Handling of specimens

See lab manual.

9.2 Blood withdrawal and biomarker studies

9.2.1 ctDNA

There is evidence that ctDNA obtained from blood specimens of advanced cancer patients may be representative of the mutational status of DNA from tumor cells and may identify the emergence of treatment resistance prior to radiographic progression.⁶⁷ 2 X 10 ml EDTA will be drawn on days 1, cycle 1 day 10+- 2 days and cycle 5, day 1 (day 85) +/- 7days. A further sample will be collected at progression. Whole blood samples should be processed (double spun) within 4 hours of collection to separate cells from plasma. Plasma Serum samples will be stored at -80°C until batched transfer to biospecimens program. Cell free DNA will be analyzed for circulating tumour DNA quantitative analysis. This testing will be performed by the [name] at OICR.

9.2.2 Germline analysis

Blood draw at C1D1 will also be used to obtain a buffy coat for DNA extraction and germline analysis. Sample should be transferred to OICR and stored at -80°C for further processing.

9.2.3 Methylation profiling

Plasma separated from samples at time-points in 9.2.1 will also be used for DNA methylation profiling. 1ml of plasma will be delivered to the [name] laboratory. Methods to be described in laboratory manual.

9.2.4 Cytokine analysis

1 x 10ml EDTA sample will be collected Cycle 1, Day 1, Cycle 1 Day 5, Cycle 1 Day 10+-2, Cycle 3 Day 1, Cycle 5 Day 1 and at progression (+/- 7 days). Whole blood samples should be processed (double spun) within 4 hours of collection to separate cells from plasma. Plasma Serum samples will be stored at -80°C until batched transfer to biospecimens program. Expression of clinically relevant cytokines will be measured using a multiplexed electrochemiluminesce (ECL) immunoassay manufactured by Meso Scale Diagnostics, and performed at the [name] at the University Health Network. We will specifically look for cytokines reflective of an abscopal effect.

10. STUDY CALENDAR

Baseline (pre-study) evaluations are to be conducted within 14 days prior to start of protocol therapy, unless specified differently in the study calendar. Scans (including tumor measurements) x-rays, informed consent, tumor biopsy, and hepatitis testing must be done \leq 28 days prior to the start of therapy. In the event that the subject's condition is deteriorating, laboratory evaluations should be repeated within 48 hours prior to initiation of the next cycle of therapy. Some visits might be conducted remotely and / or some assessments might be deferred as per physician discretion. Some of the safety lab assessments may also be done at external or community laboratories as applicable. In such cases, sites should provide Normal reference ranges of such lab and lab licenses to the Central Office.

The following schedule of assessments applies to all subjects. More frequent assessments should be obtained if clinically indicated. If pre-study laboratory and clinical assessments were done within 5 days prior to treatment initiation, they do not need to be repeated for cycle 1 day 1. For subsequent cycles 2+, day 1 assessments can be completed up to 4 days prior to day 1. A cycle is 21 days long for the purposes of this protocol.

		Cycle 1				Cycle 2	Cycle 3	Cycle 4	Cycle 5	Cycle 6+	Off Treatment Visit ^c	Survival Follow-Up ^c
		Pre-Study	Day 1	Day 2	Day 5	Day 10	Day 1	Day 1	Day 1	Day 1		
Pembrolizumab		A					A	A	A	A		
SBRT			B-----B									
Informed consent (Main and Optional)	X											
Demographics	X											
Medical history	X											
TNM Staging, BCLC Staging	X											
Vascular Thrombosis Staging ^f	X											
Concurrent meds	X	X-----X										
Physical exam	X	X		X ^e		X	X	X	X	X		
Vital signs ^d	X	X	X	X ^e		X	X	X	X	X		
Height	X											
Weight	X	X				X	X	X	X	X		
Performance status	X	X	X			X	X	X	X	X		
Child-Pugh Score	X	X		X ^e		X	X	X	X	X		
ALBI Score	X	X		X		X	X	X	X	X		
CBC w/diff, PT/INR	X	X		X ^e		X	X	X	X	X		
Neutrophil-Lymphocyte Ratio	X	X		X		X	X	X	X	X		
Serum chemistry ^a	X	X		X ^e		X	X	X	X	X		
T3 and TSH	X	X					X		X			
Hepatitis B Testing ^g	X											
Hepatitis C Testing ^h	X											

Anti-HDV Testing ^j	X										
ECHO	X										
EKG	X										
Adverse event evaluation				X-----			X		X		
Tumor measurements	X				X ^m					X ⁱ	
					Documentation (radiologic) must be provided for subjects removed from treatment for progressive disease.						
Radiologic evaluation	X					X ^m				X ⁱ	
B-HCG	X ^b										
AFP	X	X			X	X	X	X	X	X	
Biopsy for correlative studies	X										
Optional biopsy for correlative studies					X ^k						
Blood for ctDNA/methylation ^l		X		X				X		X	
Blood for cytokine analysis ^l		X		X	X	X		X		X	
Survival status											X

All assessments may be performed up to 2 working days prior to scheduled day.

A: Pembrolizumab 200 mg IV Q3W
 B: SBRT as per Section 5.1.2, commencing Cycle 1 Day 2, consisting of 5 fractions over 5-15 days
 a: Albumin, alkaline phosphatase, total bilirubin, bicarbonate, calcium, chloride, creatinine, glucose, LDH, phosphorus, potassium, total protein, AST, ALT, sodium.
 b: Serum pregnancy test (women of childbearing potential).
 c: See Section 5.4 for post-treatment follow-up requirements.
 d: Blood pressure, temperature, pulse, O₂ saturation, and respiratory rate.
 e: Day of assessment while on SBRT may vary due to weekends, but should be as close to day 3 as possible.
 f: See Appendix 4 for vascular thrombosis staging chart.
 g: All patients should have baseline Hepatitis B screening which should include: HbsAg, Anti-Hbs and Anti-Hbc (total+IgM). For patients with known hepatitis B, or if they have been deemed infected through baseline screening, additional test should include: HBV viral load (DNA), HbeAg and Anti-Hbe. If HBV viral load has been performed within previous 3 months a repeat test is not required. If Hepatitis B Testing has been performed for eligibility less than 28 days prior to start of therapy it is not required to be repeated again as a part of Baseline (Pre-study) evaluations.
 h: All patients should have baseline Hepatitis C screening which should include: Anti-HCV. For patients with known hepatitis C, or if they have been deemed infected through baseline screening, HCV viral load (RNA) should be performed. If HCV viral load has been performed within previous 3 months a repeat test is not required. If Hepatitis C Testing has been performed for eligibility less than 28 days prior to start of therapy it is not required to be repeated again as a part of Baseline (Pre-study) evaluations.
 i: Patients who come off study treatment for reasons other than radiological progression are to have tumor measurements and disease response evaluated every 3mo ± 14 days until documented progression per iRECIST or start of new therapy.
 j: Only required if the patient has a known history of Hepatitis B and the testing has not been completed previously. If testing has been done previously, a repeat test is not required. If Anti-HDV Testing is required, this must be done ≤ 28 days prior to the start of therapy.
 k: Optional biopsy to be done between 3-6 weeks on study for patients that have consented to procedure
 l: Research bloods to be drawn prior to Pembrolizumab administration. Research blood must be collected on-site at Princess Margaret Cancer Centre.
 m: Radiologic evaluation and tumor measurements should be performed at 12 weeks on treatment and then repeated every 10 weeks thereafter (± 2 weeks). CT scans should be performed at planned time points regardless of any dose delays.

11. MEASUREMENT OF EFFECT

11.1 Antitumor Effect – Solid Tumors

For the purposes of this study, subjects should be re-evaluated for response every 12 weeks. In addition to a baseline scan, confirmatory scans should also be obtained 4-8 weeks following initial documentation of objective response.

Note, response in the irradiated volume is challenging to assess before 3 months post radiation therapy due to radiation change in the surrounding liver. Even at 3 months, changes in the surrounding liver around the HCC may represent radiation treatment change, rather than tumor progression. Thus, review of images by experienced radiologists is required, as is importance of relaying radiation information to the radiologists, to avoid inaccurate labeling of progression when liver changes are due to radiation effect on the liver.

Response and progression will be evaluated in this study using both RECIST 1.1 and the new criteria proposed by immune modified Response Evaluation Criteria in Solid Tumors (iRECIST) guideline (Seymor 2017). Changes in the largest diameter (uni-dimensional measurement) of the tumor lesions and the shortest diameter in the case of malignant lymph nodes are used in the iRECIST criteria. Overall response will be assessed, as well as response in lesions outside the SBRT treatment field. These criteria keep the uni-dimensional measurement of RECIST, but incorporate the concept of unconfirmed progression (iUPD) noted with the use of immunotherapy. In the case of new lesions, assessments continue as per RECIST 1.1 but are recorded in a separate case report form. Contrasting to RECIST 1.1 new lesions may result in iUPD but immune confirmed progression (iCPD) is only assigned on the basis of this category if at next assessment additional new lesions appear or an increase in size of new lesions is seen (≥ 5 mm for sum of new lesion target or any increase in new lesion non-target); the appearance of new lesions when none have previously been recorded, can also confirm iCPD. iUPD may occur before iPR, iCR or iSD, in contrast to RECIST 1.1 where progression could not occur. Notable in this study, radiated lesions will be counted as part of the response criteria, an exception to the rules of RECIST 1.1.

11.1.1 Definitions

Evaluable for toxicity. All subjects will be evaluable for toxicity from the time of their first treatment with pembrolizumab.

Evaluable for objective response. Only those subjects who have measurable disease present at baseline, have received at least one cycle of therapy, and have had their disease re-evaluated will be considered evaluable for response. These subjects will have their response classified according to the definitions stated below. (Note: Subjects who exhibit objective definitive disease progression prior to the end of cycle 1 will also be considered evaluable.)

Evaluable Non-Target Disease Response. Subjects who have lesions present at baseline that are evaluable but do not meet the definitions of measurable disease, have received at least one cycle of therapy, and have had their disease re-evaluated will be considered evaluable for non-target disease. The response assessment is based on the presence, absence, or unequivocal progression of the lesions. For

iUPD, iCPD will need to be confirmed by repeat imaging 4-8 weeks after iUPD was identified, as per iRECIST.

11.1.2 Disease Parameters

Measurable disease. Measurable lesions are defined as those that can be accurately measured in at least one dimension (longest diameter to be recorded) as ≥ 20 mm by chest x-ray or as ≥ 10 mm with CT scan, MRI, or calipers by clinical exam. For nodal lesions, see criteria below. All tumor measurements must be recorded in millimeters (or decimal fractions of centimeters).

Tumor lesions treated with SBRT as part of the study protocol will be considered measurable for the primary analysis. Other previously irradiated lesions will not be considered measurable.

Malignant lymph nodes. To be considered pathologically enlarged and measurable, a lymph node must be ≥ 15 mm in short axis when assessed by CT scan (CT scan slice thickness recommended to be no greater than 5 mm). At baseline and in follow-up, only the short axis will be measured and followed.

Non-measurable disease. All other lesions (or sites of disease), including small lesions (longest diameter < 10 mm or pathological lymph nodes with ≥ 10 to < 15 mm short axis) as well as truly non-measurable lesions. Lesions considered truly non-measurable include: leptomeningeal disease, ascites, pleural/pericardial effusions, lymphangitic involvement of skin or lung, inflammatory breast disease, abdominal masses/abdominal organomegaly identified by physical exam that is not measurable by reproducible imaging techniques.

Vascular thrombosis will be considered non-measurable disease, unless vascular HCC is the only HCC present. In this case, vascular response guidelines in 11.1.4.3 should be used.

Note: Cystic lesions that meet the criteria for radiographically defined simple cysts should not be considered as malignant lesions (neither measurable nor non-measurable) since they are, by definition, simple cysts.

‘Cystic lesions’ thought to represent cystic metastases can be considered as measurable lesions, if they meet the definition of measurability described above. However, if non-cystic lesions are present in the same subject, these are preferred for selection as target lesions.

Target lesions. All measurable lesions up to a maximum of 2 lesions per organ and 5 lesions in total, representative of all involved organs, should be identified as **target lesions** and recorded and measured at baseline. Target lesions should be selected on the basis of their size (lesions with the longest diameter), be representative of all involved organs, but in addition should be those that lend themselves to reproducible repeated measurements. Vascular thrombi will not be selected as target lesions, unless vascular HCC is the only HCC present. It may be the case that, on occasion, the largest lesion does not lend itself to reproducible measurement in which circumstance the next largest lesion which can be measured reproducibly should be selected. A sum of the diameters (longest for non-nodal lesions, short axis for nodal lesions) for all target lesions will be calculated and reported as the baseline sum diameters. If lymph nodes are to be included in the sum, then only the short axis is added into the sum. The baseline sum diameters will be used as reference to further characterize any objective tumor regression in the

measurable dimension of the disease. Radiated lesions can be counted as target lesions provided there has been demonstrated progression in the lesion.

Non-target lesions. All other lesions (or sites of disease) including any measurable lesions over and above the 5 target lesions should be identified as **non-target lesions** and should also be recorded at baseline. Measurements of these lesions are not required, but the presence, absence, or in rare cases unequivocal progression of each should be noted throughout follow-up.

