5. TREATMENT PLAN

5.1 Agent Administration

Treatment will be administered on an outpatient basis. Appropriate dose delays and management of adverse events are described in Section 6. No investigational or commercial agents or therapies other than those described below may be administered with the intent to treat the subject's malignancy.

Regimen Description			
Agent	Dose	Route	Schedule
Pembrolizumab	200 mg	IV over 30 minutes	Every 3 weeks
SBRT administered to dominant hepatic HCC			Starting day 2 of cycle 1 pembrolizumab, given in 5 fractions over 5-15 days

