5.1.2 Stereotactic Body Radiotherapy (SBRT) Dosing and Scheduling

All the definite HCC with vascular invasion should be treated by SBRT when safe, up to a maximum of 10 lesions and total diameter of ≤ 20 cm. However, extrahepatic HCC, all satellites of HCC and non-definite HCC need not be encompassed within the irradiated volumes, especially if normal tissue dose limits cannot be met.

Treatment will be delivered in 5 fractions. The time between fractions should be between 24 and 72 hours, with treatment delivered to all targets over 5 to 15 days (starting on day 2, as per the schema). The preferred inter-fraction interval is 24 hours, with the exception of when luminal OARs are at their maximal dose, when it is preferred that the first two fractions are to be delivered on day 2 and 3 and other fractions every other day. All lesions may be treated on the same day, or alternative lesions may be treated on alternate days, as long as the overall treatment time is 15 days at maximum.

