13.4 Analysis of Secondary Endpoints

Response in non-irradiated lesions

Response in non-irradiated lesions is defined as the proportion of subjects in the study population who demonstrate iCR or iPR, by iRECIST 1.1, when tumors within the radiotherapy treatment field are excluded from analysis. Subjects will be ineligible for this analysis if no RECIST-measurable lesions exist outside the radiotherapy treatment field.

The point estimate and 95% confidence interval for ORR will be provided using the Clopper and Pearson exact binomial method.

Duration of Response (DOR)

For subjects who demonstrate iCR or iPR, by iRECIST, DOR is defined as the time from first documented evidence of iCR or iPR until disease progression or death due to any cause, whichever occurs first.

DOR will be estimated by the Kaplan-Meier method, and the Cox proportional hazard regression model will be used to analyze the effects of factors, in addition to treatment, that may be associated with DOR.

Progression-Free Survival (PFS)

PFS is defined as the time from enrollment until the date of objective disease progression, by iRECIST, or death (by any cause in the absence of progression).

PFS will be estimated by the Kaplan-Meier method, and the Cox proportional hazard regression model will be used to analyze the effects of factors, in addition to treatment, that may be associated with PFS.

Overall Survival (OS)

OS is defined as the time from study enrollment to death due to any cause.

OS will be estimated by the Kaplan-Meier method, and the Cox proportional hazard regression model will be used to analyze the effects of factors, in addition to treatment, that may be associated with OS.

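### The single, capped target-lesion set can leave unirradiated liver lesions unmeasured, so some subjects counted for out-of-field response have no route to iPR

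*Combined protocol and SAP*

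**What the plan says.** **Lesion selection (11.1.2).** Target lesions are "All measurable lesions up to a maximum of 2 lesions per organ and 5 lesions in total". On the order of choice: "Target lesions should be selected on the basis of their size (lesions with the longest diameter), be representative of all involved organs". Lesions treated with protocol SBRT are not barred: "Tumor lesions treated with SBRT as part of the study protocol will be considered measurable for the primary analysis". A condition follows: "Radiated lesions can be counted as target lesions provided there has been demonstrated progression in the lesion". Section 13.3 repeats that condition. Everything else is non-target, and for those lesions "Measurements of these lesions are not required, but the presence, absence, or in rare cases unequivocal progression of each should be noted".

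**Where the radiation goes.** The regimen table in 5.1 reads "SBRT administered to dominant hepatic HCC". Section 5.1.2 allows up to 10 lesions to be treated and adds that "extrahepatic HCC, all satellites of HCC and non-definite HCC need not be encompassed within the irradiated volumes".

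**The out-of-field endpoint.** Secondary objective 1 (section 1.2) is the response rate in non-irradiated lesions, as an estimate of the abscopal effect. Section 13.4 defines it as iCR or iPR once in-field tumours are set aside, and says: "Subjects will be ineligible for this analysis if no RECIST-measurable lesions exist outside the radiotherapy treatment field". Section 13.6.2 defines the analysis population in the same way. Neither section asks for an out-of-field target lesion.

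**Response categories (11.1.4).** PR requires a fall of at least 30% in the sum of the target lesions. The part of Table 10 for subjects with non-target lesions alone offers CR, non-CR/non-PD, NE and PD. Both iPR rows of Table 11 require target lesions in iCR or iPR.

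**The concern.** Two selection rules point at the same lesions. Targets in the liver are the largest ones, and SBRT is aimed at the dominant ones. When at least two progressing liver tumours are irradiated, they can take both liver target slots. A smaller unirradiated liver lesion that still meets the measurability threshold then falls to non-target status, and no diameter has to be recorded.

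The out-of-field analysis nevertheless counts that subject, because its entry rule looks at whether a measurable lesion exists and not at whether one is followed by measurement. Once the in-field tumours are removed, nothing with a required measurement is left and a partial response cannot be derived.

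At stake is the trial's only direct estimate of the abscopal effect. Exploratory objective 4 (cytokines as predictors of that effect) relies on the same classification. The protocol foresees the situation: exploratory objective 2 compares subjects with all and with not all tumour deposits irradiated. The independent review in 11.1.6 covers iCR and iPR only, so it would not pick up a response that was never scored.

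**Working it through.** **1. The plan's own figure.** The documents give no size, power or expected rate for the out-of-field endpoint. The only design figure is the primary one in 13.2: 10 then 22 evaluable subjects, continue with 2 or more responses, success with 6 or more, 15% against 40%. The exact probability of success is

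Σ (x = 2 to 10) P(X₁ = x) · P(X₂ ≥ 6 − x), with X₁ ~ Bin(10, p) and X₂ ~ Bin(12, p).

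- p = 0.15: 0.0907, within the stated one-sided 10%.
- p = 0.40: 0.9031, meeting the stated 90%.

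The primary design reproduces. It uses none of the out-of-field rules, so nothing below alters it.

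**2. Rule trace.** Take a subject with liver lesions A, B and C in falling order of size, all at least 10 mm, and no measurable extrahepatic disease. A and B are irradiated and have shown progression. C is left out of the SBRT volume.

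| Step | Rule | Result |
|---|---|---|
| Choose targets | 11.1.2: two per organ, by size | A and B |
| Classify C | 11.1.2: beyond the cap | Non-target; diameter not required |
| Enter out-of-field population | 13.4, 13.6.2: measurable lesion outside the field | Yes, because of C |
| Remove in-field tumours | 13.4 | A and B go; C remains |
| Score iPR | 11.1.4: needs a target sum (Table 11: target in iCR or iPR) | Not possible |
| Score iCR | 11.1.4: disappearance of disease and normal tumour markers | Still possible |

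Three variations take a subject out of the problem:

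- Measurable extrahepatic disease normally supplies an out-of-field target, since targets must represent all involved organs within the total of five.
- If A or B has not shown progression, the condition in 11.1.2 and 13.3 can free a liver slot for C.
- If C is irradiated too and nothing else is measurable, the subject is outside the analysis.

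**3. Size.** Let p be the true out-of-field response rate and f the share of the denominator in the position traced above. If those subjects count as non-responders and iCR is rare, the expected observed rate is p × (1 − f). Both p and f are assumptions. With p = 20%:

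- f = 10%: 0.20 × 0.90 = 18%
- f = 30%: 0.20 × 0.70 = 14%
- f = 50%: 0.20 × 0.50 = 10%

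**4. The same effect in counts (hypothetical).** Suppose 15 subjects enter, 3 cannot be scored iPR, and 3 of the others respond. With all 15 kept, 3/15 = 20% (Clopper-Pearson 95% CI 4.3% to 48.1%). With the denominator limited to subjects who have a measured out-of-field lesion, 3/12 = 25% (5.5% to 57.2%). Here f = 3/15 = 20%, and 25% × 0.80 = 20%, which agrees with the formula. The intervals overlap heavily, so with these numbers the shift is small next to sampling error.

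**The case against.** The strongest reply is that 13.4 can be read as re-selecting targets after in-field tumours are excluded. Applying 11.1.2 to what remains would make C a target. Section 11.1.1 supports this, since it describes non-target evaluation for lesions that fail the definition of measurable disease, and C meets that definition. The introduction to 11.1 also lists out-of-field response as something to be assessed, and saying that a measurement is not required does not forbid it. This reading is possible, but no section states it. No out-of-field baseline sum, target list or measurement duty is given, and a site that follows 11.1.2 to the letter need not record C's diameter.

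It is also fair to say that the endpoint is secondary and descriptive, that no decision rule depends on it, and that missing diameters could be read later from the scheduled scans by the independent radiologist mentioned in 2.3. All of that stands and limits the importance of the point. A later reading is weaker than a prospective one, though, unless the lesions are chosen without sight of follow-up.

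A reader might infer that the two largest irradiated lesions always occupy the liver slots. The demonstrated-progression condition, and the preference for lesions that can be measured reproducibly, mean that this holds in some subjects only.

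**Conclusion.** The point holds as a gap between three rules: how targets are chosen, which lesions are irradiated, and who enters the out-of-field analysis. As written, they allow a subject into the denominator who can reach iCR but not iPR. It applies only where both liver targets are irradiated and the sole measurable out-of-field disease is a further liver lesion. It should be repaired before the abscopal rate is analysed. The primary endpoint, its error rate, its power and the 22 evaluable subjects are untouched.

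Two stronger conclusions are tempting and not supported:

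- **A certain downward bias.** Section 13.6.2 counts missing data as non-response for the primary endpoint only, and its category 8 allows a subject to be not assessable. If affected subjects are coded as failures, the rate falls by the factor (1 − f). If they are coded as not assessable, the cost is lost information.
- **A large affected share.** A reader might infer this from the 12% extrahepatic disease in the centre's earlier SBRT series (section 2.2.2). That figure does not give f. Subjects without extrahepatic disease enter the denominator only if a measurable liver lesion was left unirradiated, and SBRT may cover up to 10 lesions. The series is also not described as a population treated after a TKI. The documents contain no count from which f could be estimated, so the 18%, 14% and 10% above are illustrations.

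**What to change.** Keep the primary target set as it is.

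- **11.1.2:** add a second baseline set of out-of-field targets, up to 2 per organ and 5 in total, chosen only from measurable lesions outside the planned SBRT volumes and measured on every scheduled scan.
- **Subjects already enrolled:** choose this set from the baseline images and SBRT plans, without sight of follow-up scans. The synopsis already provides for archiving baseline and planning imaging.
- **13.4 and 13.6.2:** derive response in non-irradiated lesions from this set, and define the population as subjects with at least one such target at baseline.
- **Later SBRT:** section 5.3.2 permits further SBRT to oligoprogressive lesions. State that a lesion irradiated under that section does not contribute to out-of-field response after that date. Otherwise shrinkage from direct radiation could be counted as abscopal.

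The cost is an amendment, one eCRF page and a few extra diameters per existing scan. No additional scans, visits or subjects are needed.
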